#### **With respect to the GODIVA-bone substudy;**

Development of prediction model: A multivariable prediction model will be developed to predict the response after KD treatment. Separate analyses for clinical success (defined as 15 points improvement in WOMAC pain), radiographic success (any increase in minimal JSW (>0 mm)) and success both clinically and radiographically will be performed. Also, more stringent cut-offs will be used e.g. based on the minimal detectable change. Model building will be performed stepwise starting with the predictive parameters that are more easily accessible in regular clinical practice (e.g. demographics and scores of bone parameters) as predictors, and thereafter the more demanding parameters (i.e. continuous scores, parameters derived from more sophisticated imaging modalities) are added. The total set of parameters to use as predictors in multivariable modelling will be decided based on initial findings (e.g. analysis during the third stage as described above), external findings from e.g. literature as well as clinical and biological expertise.

The modelling technique to use will be determined by experimentation, predictive performance, robustness, and 'explainability' of models and will be decided in discussion with clinicians, epidemiologists, data scientists and patients to ensure that the resulting models are statistically adequate and clinically useful.

All prediction models will be developed and externally validated (e.g. by using 2/3 of the data for development (including cross-validation for internal validation) and the remaining data as external validation data).

All data handling procedures and analyses to be performed, including the handling of missing data, specific features to be developed, and algorithms to use will be described in

a Statistical Analysis Plan (SAP) before 'database lock'. This SAP will be finalized in cooperation with the methodologists from our department and from the Julius Center with which we cooperate in several other projects. Models will be developed and reported according to the TRIPOD criteria [Collins G et al. BMC Medicine 2015;13,].

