**Objective:** To determine whether KJD is non-inferior on patient reported effectiveness as compared to a KP (i.e. usual care) for relatively young patients with end-stage knee OA. In the GODIVA bone substudy, the primary objective is to predict the benefit from knee distraction treatment by peri-articular bone characteristics. The secondary objective of the substudy is understanding the change in peri-articular bone in relation to the benefit from knee distraction treatment (pain relief and cartilage repair) by expanding the pre-treatment data with follow-up data.

**Study design:** Pragmatic, open, randomized, multi-centre, non-inferiority trial with 24 months follow-up.

**Study population:** 1,200 knee OA patients  $\leq 65$  year of age, indicated for a KP will be randomized (1:1) to KJD or KP. For the GODIVA-bone substudy: 200 patients from the 600 patients randomised to treatment with knee distraction in the GODIVA trial will be included.

**Intervention (if applicable):** KP is indicated and surgically implanted according to regular clinical practice (can be a total- or unicompartmental KP, in line with local practice in consultation with the patient and conform the national guideline by Dutch orthopaedic society (NOV)). KJD treatment is performed according to the current approved concept NOV recommendations for clinical practice.

**Main study parameters/endpoints:** Primary endpoint: Western Ontario and McMaster Universities Arthritis Index (WOMAC) total score. Main secondary outcomes: WOMAC/KOOS Pain, stiffness, and physical function sub-scores, quality of life (EQ-5D, SF-36), radiographic joint space width (KJD only) as a surrogate for cartilage tissue repair; adverse events, and productivity and healthcare cost. All assessed over 24 months.

For the GODIVA-bone sub-study the main parameters are MRI, CT, and DEXA image markers and blood and urine biochemical markers at baseline and 24 months.

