#### 4.4 Sample size calculation

In the recently performed 'StWP' evaluation of KJD by 'Zorg Instituut Nederland (ZiN)' a non-inferiority limit for the 'crucial' endpoint of total WOMAC score at 2 years (the primary endpoint here) was defined at 15.

Assuming a 'true' difference in total WOMAC score of 12 points in favor of KP based on previous (pilot) data with an SD of 15 (14), 527 patients need to be recruited into each arm to obtain 90% power (2.5% one-sided significance) to demonstrate 'non-inferiority' (calculated using the power procedure in SAS 9.4). To account for missing data and loss to follow-up, we increase the sample size with ~15% and will include 600 patients per group.

**Sample size considerations for the GODIVA-bone substudy:** The response outcomes to use for the prediction models have an occurrence between ~30% and ~50%, indicating that with the 200 patients included (2/3 responder, i.e. 134 patients) we will have between 60 and 100 events for our analysis (between 40 and 67 for model development). Based on general rule of thumb, where at least 5-10 events per variable studies are needed we will have room for maximally 13 predictive parameters. To adhere to this, when needed, we will use data reduction techniques (e.g. principal component analysis or other feature reduction/selection techniques) or analysis techniques, suitable for sparse data, like penalized regression techniques to be defined in the SAP. For the secondary aim (explorative) we will relate changes in bone parameters to changes in pain (WOMAC pain) and cartilage tissue repair (radiographic joint space width increase) over a period of two years. The same parameters as explored in the predictive analysis as well as changes therein will be used as independent variables in this analysis.

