### **5.3 Escape medication (if applicable)**

Not applicable. Patients may use (pain) medication (which will be recorded) according to regular care NOV and participating institute guidelines/recommendations. If needed further surgical interventions (e.g. arthroplasty or revision for KJD and KP) in line with regular care, NOV and local guidelines will be performed (and registered).

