**In the second stage of the GODIVA-bone substudy**, bone parameters will be measured as continuous parameters, which is more time consuming but results in more sensitive measures. From radiographs, subchondral bone density and osteophyte size will be measured using KIDA software [Marijnissen A et al. Osteoarthr Cartil 2008;16,; Jansen M et al. Osteoarthr Cartil 2021;29,]. Bone mineral density will be measured from DEXA scans [Lo G et al. Semin Arthritis Rheum 2018;48,]. Subchondral bone density, cortical bone thickness and osteophyte volume will be measured from CT scans [Mastbergen S et al. Osteoarthr Cartil 2022;30,]. BML and cyst volume will be measured from MRI scans [Roemer F et al. Osteoarthr Cartil 2010;18,].

**In the third stage of the GODIVA-bone substudy**, image classification machine learning models (like convolutional neural networks) will be used for all imaging types to classify (in our case predict) which patients will be clinical and/or structural responders. These models can be used restricted (i.e. the model can only look at bone) and unrestricted. Available baseline images will be divided in training, validation, and test sets, to develop and confirm results of machine learning algorithms. At present we have gained experience in this approach by ML using images of PsA patients [Arbabi S et al. 2022; ms in preparation]. Final algorithms can not only be used directly for prediction; looking at which parts of the images are most important for the ML model provides additional information on which (bone) sites and properties are important for clinical and/or structural response and thus allow the definition of new features or combined selection of features from imaging to use in an overall prediction model (see below).

For biochemical data we will use serum/plasma samples and urine samples. When all baseline samples are collected, the state-of-the-art selection of bone biomarkers at that time will be made, together with experts in the field (Nordic Bioscience), and analysed (within feasibility with respect to costs).

Where relevant these results will be integrated with the endpoint analyses of the GODIVA trial.

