5. The clinical checks after surgery will be performed in line with local clinical practice. According to regular practice, patients treated with Knee prosthesis will visit the orthopaedic surgeon at ~6 and ~12 months after surgery for a clinical check. Patients treated with Knee Joint Distraction will visit the orthopaedic surgeon after ~3 weeks for a clinical check, at 6 weeks for removal of the distraction frame, and at ~6 months and at ~12 months after surgery for a clinical check. Although the clinic visits for check-up are not part of the study visits and follow regular care practice at the local center (and thus are not specifically depicted in above scheme), data on adverse events occurring will be specifically collected during the regular care visits in a standardized way (continuous registration, via standard notation in electronic health records and entered in Castor via EHR review). This is also the case for the standard measurement of knee flexion. Questionnaires will be sent to all participants via email (via Castor EDC) at 3 weeks and at 2, 5, 8, 12 and 24 months after surgery/start distraction period). At 12 and 24 months after surgery, only patients treated with joint distraction will be invited to come to the hospital for a radiograph of the knee (after 12 months is part of regular care according to NOV recommendations). At 24 months all patients will be contacted and asked if any additional surgical procedures of the knee have been performed or planned, which will be noted.

6. In case of early study termination, a phone call will be made to ask for the reason of termination and ask if any additional surgical procedures of the knee have been performed or planned.

**For the GODIVA-bone substudy:** Standard(ised) knee-MRI (single clinical time slot comprising 3 sequences), standard(ised) knee-CT, standard(ised) DEXA (according to the Imaging manual of the substudy), vena puncture for 2 times 7 cc blood and a urine sample will be collected at baseline and 2 years after treatment. Imaging and sampling will be performed as much as possible during the visits of the GODIVA study. Only for a limited number of patients extra visits may be needed.

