#### 9.2.2 Serious adverse events (SAEs)

A serious adverse event is any untoward medical occurrence or effect that

- results in death;
- is life threatening (at the time of the event);
- requires hospitalisation or prolongation of existing inpatients' hospitalisation;
- results in persistent or significant disability or incapacity;
- is a congenital anomaly or birth defect; or
- any other important medical event that did not result in any of the outcomes listed above due to medical or surgical intervention but could have been based upon appropriate judgement by the investigator.

An elective hospital admission will not be considered as a serious adverse event.

The investigator will report all SAEs to the sponsor without undue delay after obtaining knowledge of the events.

The sponsor (UMCU) will report the SAEs through the web portal *ToetsingOnline* to the accredited METC that approved the protocol, within 7 days of first knowledge

for SAEs that result in death or are life threatening followed by a period of maximum of 8 days to complete the initial preliminary report. All other SAEs will be reported within a period of maximum 15 days after the sponsor has first knowledge of the serious adverse events.

Exceptions to above SAE reporting to the accredited METC are the following expected, pre-determined SAEs (although these of course will be documented):

- o a KP or revision surgery of the index knee within 2 years after (failure of) the KJD/KP treatment
- o With respect to KJD, a pin tract infection for which the patient is treated temporarily with intravenous antibiotics

These SAEs will be reported in line listings, in annual progress reports.p

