### **11.4 Benefits and risks assessment, group relatedness**

The benefits and risks for the patients treated with KP are fully according to clinical practice. Patients should realize that in the Netherlands KJD is still not reimbursed and is only provided within the setting of the current clinical trial.

The benefit of a KP over KJD might be the swifter and slightly better clinical effect of treatment although at the expense of the original joint and with the higher risk of revision surgery later in life. The benefit of the KJD over a KP is that the original joint is preserved with the chance of postponing placement of a KP and decreasing the chance of revision surgery later in life, although with the burden of a 6-week distraction period with the chance of skin pin-tract infections, and possibly a slightly (non-clinically relevant) lesser clinical benefit.

In both arms, at 7 moments questionnaires must be filled out without the need of a clinic visit. At baseline for both treatments, and in case of KJD treatment additionally at 24 months a clinic visit takes place (the latter for a study specific x-ray) in addition to the typically 4 clinic visits performed in regular practice. In both arms a comparable number of knee radiographs is made in regular care and for KJD the 24 months study specific x-ray will be made.

In both arms the chance of failure is <5% in the first year after treatment. Failure can be due to multiple reasons, mostly persisting pain, leading to either revision surgery in case of a KP or placement of a first KP in case of KJD. Additionally, there is a chance of infection in both arms. In case of KJD these are primarily superficial skin pin tract infections, in generally successfully treatable with oral antibiotics. In both arms a small chance for deeper infections up to osteomyelitis are seen, needing i.v. antibiotics and/or nettoyage or even removal of the frame in case of KJD or early revision surgery in case of KP. Rehabilitation after the intervention(period) is similar for both treatment arms.

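### The bone substudy's clinical-success label makes no exception for a knee replaced before assessment, so a distraction failure relieved by a prosthesis can count as a responder to distraction

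*Protocol*

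**What the plan says.** The Summary gives the substudy's purpose: "the primary objective is to predict the benefit from knee distraction treatment by peri-articular bone characteristics". Section 10.3 turns this into outcomes and plans "Separate analyses for clinical success (defined as 15 points improvement in WOMAC pain"), together with radiographic success (any gain in minimal joint space width) and success on both. It adds that stricter cut-offs will also be tried. It sets no condition on surgery to the index knee between distraction and scoring.

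The responder status has a second use. In Section 8.1.4 the third-stage image models are meant "to classify (in our case predict) which patients will be clinical and/or structural responders".

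Four other places bear on a knee that is replaced during follow-up:

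- Section 11.4 and the Summary describe failure after KJD, mostly from persisting pain, as leading to a first KP. They state: "In both arms the chance of failure is <5% in the first year after treatment".
- Section 9.2.2 lists among the expected serious adverse events "a KP or revision surgery of the index knee within 2 years after (failure of) the KJD/KP treatment".
- Section 5.3 provides for later surgery in regular care: "If needed further surgical interventions (e.g. arthroplasty or revision for KJD and KP"), to be performed and registered.
- Section 8.3 keeps data coming: "Questionnaires will be sent to all participants via email (via Castor EDC"), the last at 24 months. Section 8.4.1 names no withdrawal criteria, so a conversion does not end follow-up.

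On size, Section 4.4 expects that "we will have between 60 and 100 events for our analysis (between 40 and 67 for model development").

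**The concern.** The protocol uses a first KP after distraction as the mark of failure, yet the success rule looks only at a pain score that such a patient can still supply. The Introduction describes a total prosthesis as effective against pain, so a 15-point gain after conversion is plausible. The patient then enters the model as someone who benefited from distraction, although the benefit came from the prosthesis.

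These errors would not be spread at random. They fall on failures, the patients a model for shared decision-making most needs to recognise. Bone features that go with failure would be partly credited to success, and the image models would be trained on the same labels. Stricter cut-offs do not remove the problem, because a prosthesis can also produce a larger gain.

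**Working it through.** **1. Does the text allow the mislabelling?** The chain has four links, each in the protocol:

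- A KP can follow KJD within the two years (5.3, 9.2.2).
- The protocol regards this as failure (Summary, 9.2.2, 11.4).
- Pain is still collected afterwards (8.3, 8.4.1).
- The success rule consults only the change in pain (10.3).

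No section sets aside or recodes a pain score obtained after a KP for this label. Section 10.3 leaves data handling, missing data, features and algorithms to the substudy SAP. A score after conversion is observed, so a missing-data rule would not necessarily reach it.

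**2. Which labels are exposed?** Clinical success is. Radiographic and combined success need a native joint space, which a replaced knee cannot supply. The protocol does not say how such a knee is scored, but a false success is not the natural reading there.

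**3. The plan's own event counts (4.4).** With 200 patients and response in about 30% to 50%:

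- All patients: 200 × 0.30 = 60 and 200 × 0.50 = 100.
- Development set of 134: 134 × 0.30 = 40.2 and 134 × 0.50 = 67.
- Predictors at 5 events each: 67 / 5 = 13.4, so 13.

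All of these agree with the protocol.

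**4. Number mislabelled.** Formula: N × f × r. Here f is the share given a KP before assessment, and r is the share of those who reach 15 points on WOMAC pain. Both are assumptions: f = 2-5%, r = 50-100%. The protocol gives only a first-year failure bound of 5% and no 24-month rate.

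| | Low (f = 2%, r = 50%) | High (f = 5%, r = 100%) |
|---|---|---|
| Converted, of 200 | 4 | 10 |
| Mislabelled, of 200 | 2 | 10 |
| Relative to 100 events | 2.0% | 10.0% |
| Relative to 60 events | 3.3% | 16.7% |
| Mislabelled, of 134 | 1.3 | 6.7 |
| Relative to 67 development events | 2.0% | 10.0% |
| Relative to 40 development events | 3.4% | 16.8% |

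Each further percentage point of conversion adds 200 × 0.01 × (0.5 to 1) = 1 to 2 mislabelled patients.

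**5. Effect of relabelling on model size.** At the high end and 5 events per predictor:

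- From 67 events: (67 − 6.7) / 5 = 12.1, so room falls from 13 to 12 predictors.
- From 40 events: (40 − 6.7) / 5 = 6.7, so room falls from 8 to 6.

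**The case against.** The strongest reply is that this belongs in the substudy SAP, which 10.3 promises before database lock. Section 10.3 fixes a cut-off but names no assessment time, so it can be read as an outline still to be completed. Silence on conversions is compatible with a later rule that counts them as non-responders. Part of this stands: the text shows a gap, and a reader should not infer that the final analysis will mislabel anyone. It does not remove the point. What 10.3 defers does not include the success definition, which it states itself and which conflicts with the protocol's own use of a later KP as failure.

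A second objection is that 17% stacks the highest conversion, a pain response in every converted patient and the lowest event count. That is right. The 30-50% in Section 4.4 covers several response outcomes. Combined success is a subset of clinical success, so the low end may well belong to the combined outcome. The 2-10% range is the better guide.

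A reader might also infer that the main trial is biased, because patients who complete distraction and later receive a KP keep their WOMAC scores in both the per-protocol and ITT analyses of Section 10.1. The documents do not support that. Section 3 compares KJD and KP as initial treatments, and keeping later scores is consistent with such a comparison. Reinterventions are a listed outcome (8.1.2), and nothing in 10.1 claims that per-protocol against ITT isolates conversions. The direction of any shift is also unknown. Assume 2-5% conversion after KJD, 0-5% revision after KP, and gains of 10-30 points from either. The net shift in the WOMAC difference then runs from 0.02 × 10 − 0.05 × 30 = −1.3 to 0.05 × 30 − 0 = +1.5. It is 0 when rates and gains are equal in the two arms.

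**Conclusion.** The point holds for the clinical-success label of the GODIVA-bone substudy and for the third-stage models that use it. Taken literally, the definition can count a failure, in the protocol's own sense, as a response to distraction. That this can happen follows from the text; how often it would happen rests on the assumed conversion and pain-response shares. Under those assumptions the effect is modest in number, but it is concentrated in the patients who matter most to the model. If few knees are replaced before assessment, it is small. The radiographic and combined labels are not clearly affected, and the primary non-inferiority comparison is not called into question. The definition should be completed before substudy outcomes are examined.

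**What to change.** Add one sentence to Section 10.3: a substudy patient who receives a knee prosthesis in the index knee before the success assessment is classified as a non-responder for clinical success, whatever the WOMAC pain score. State in 10.3 or 8.1.4 that the third-stage image models use the same label. The substudy SAP should carry the rule over unchanged.

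No new data are needed. Reinterventions are a listed outcome (8.1.2), and all patients are asked about further knee surgery at 24 months (8.3).

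There are two downsides. Fewer events remain for model development, at most 6.7 fewer in the development set under the assumptions above. Knees replaced for reasons other than pain, such as infection, also become non-responders. No change to the main-trial analysis is proposed.

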#### 8.1.2 Secondary study parameters/endpoints (if applicable)

- WOMAC sub-scores for pain, stiffness, and function (0-100)
- KOOS scores for Pain, Symptoms, Function in daily living (ADL), Function in sport and recreation (Sport/Rec), and knee related Quality of life (QOL) (all scored on a 0-100 scale)
- SF36 physical component score and mental component score (0-100)
- NRS-pain (0-10)
- Patient Acceptable Symptom State
- NRS-satisfaction (0-10)
- EQ5D-5L for generic Quality of Life
- Pain medication (custom made questionnaire to assess the use of pain medication during the assessment period (last week) of the KOOS pain questionnaire)
- (serious) adverse events; including pin-tract infections based on a custom made CRF.
- Occurrence of surgical reinterventions (KP and revision arthroplasty procedures)
- Radiographic Joint space width (for KJD only) in millimetres using KIDA (Knee Images Digital Analysis; 15) as well as overall K-L grade from the same image.

See Appendix A – N

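### The GODIVA-bone clinical prediction model is fitted only to a yes/no cut of WOMAC pain; fitting the full score and deriving the success probability from it would use the same data better for a change of wording

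*Protocol*

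**What the plan says.** The Summary makes predicting benefit from knee distraction the primary objective of the GODIVA-bone substudy. Section 10.3 names the outcomes for that model: "Separate analyses for clinical success (defined as 15 points improvement in WOMAC pain"), any increase in minimal joint space width, and both together. It adds: "Also, more stringent cut-offs will be used e.g. based on the minimal detectable change". All of these are binary, and no prediction model with pain on its full scale is described.

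Section 4.4 sizes the work by events: "The response outcomes to use for the prediction models have an occurrence between ~30% and ~50" per cent, giving "between 60 and 100 events for our analysis (between 40 and 67 for model development"), with room for at most 13 predictors at 5-10 events per variable. It allows data reduction or penalised regression if needed.

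Section 8.1.2 lists "WOMAC sub-scores for pain, stiffness, and function (0-100") among the secondary endpoints. The schedule in section 8.3 collects the KOOS, from which WOMAC is computed, at baseline and 24 months. For the exploratory secondary aim of the substudy, section 4.4 does use the uncut score: "we will relate changes in bone parameters to changes in pain (WOMAC pain") and to joint space width, with the same bone parameters among the independent variables.

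**The concern.** Cutting the score at 15 points treats gains of 14 and 15 as opposite outcomes and gains of 15 and 60 as the same. The model then cannot use the differences among patients on the same side of the cut. In a small development set this makes marker effects and predicted probabilities less precise than the collected data allow. It also contributes to the shortage that section 4.4 has to manage: 40-67 development events rather than about 134 graded outcomes. Each stricter cut needs a further model, usually with fewer events.

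The purpose given in the Summary is a probability of success for shared decision-making. That probability can be obtained from a model of the full score, so the purpose does not require the fitted outcome to be binary.

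**Working it through.** **Inputs from the Protocol.** 200 substudy patients; occurrence about 30-50% for the response outcomes together; development share two-thirds ("by using 2/3 of the data for development (including cross-validation for internal validation) and the remaining data as external validation data"); 5-10 events per variable. Section 4.4 describes 134 as "with the 200 patients included (2/3 responder, i.e. 134 patients"). The number matches the two-thirds development share (200 × 2/3 = 133.3), so it is used here as the development set.

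**Assumed, because the Protocol gives no value.** A roughly normal pain outcome, and a correlation r between one bone marker and that outcome.

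**1. The plan's own figures reproduce.** 200 × 0.30 = 60 and 200 × 0.50 = 100 events. 134 × 0.30 = 40.2 and 134 × 0.50 = 67 development events. 67 / 5 = 13.4, so at most 13 predictors.

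**2. Information kept by the cut.** For a normal outcome and a weak marker, efficiency relative to the full score is φ(z_p)² / [p(1 − p)], where p is the success proportion and z_p the matching normal quantile.

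| Success p | Efficiency | Loss | 134 patients count as | 200 patients count as |
|---|---|---|---|---|
| 0.50 | 0.637 | 36.3% | 85 | 127 |
| 0.40 | 0.622 | 37.8% | 83 | 124 |
| 0.30 | 0.576 | 42.4% | 77 | 115 |

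The loss is smallest at p = 0.50, so about 36% is the floor whatever the true success rate. At 67% success, the literal reading of the responder phrase in section 4.4, it is 41%. If a stricter cut gave 20% success (an assumption), the loss would be 51%, with 134 × 0.20 = 27 development events. That leaves room for 5 predictors at 5 events each.

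**3. Single-marker power.** Two-sided 5%, Fisher z: noncentrality = atanh(r) × √(n − 3), multiplied by √efficiency for the cut outcome. Example with n = 134, r = 0.25, p = 0.50: 0.2554 × 11.446 = 2.923 gives 83.2%; 2.923 × √0.637 = 2.332 gives 64.5%.

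| n | r | Full score | Cut, p = 0.50 | Cut, p = 0.30 | Loss (points) |
|---|---|---|---|---|---|
| 134 | 0.10 | 20.9% | 15.0% | 14.0% | 5.9-6.9 |
| 134 | 0.20 | 64.1% | 45.7% | 42.1% | 18.4-22.0 |
| 134 | 0.25 | 83.2% | 64.5% | 60.2% | 18.7-23.0 |
| 134 | 0.35 | 98.7% | 91.6% | 88.8% | 7.1-9.9 |
| 200 | 0.10 | 29.1% | 20.2% | 18.8% | 8.8-10.3 |
| 200 | 0.20 | 81.2% | 62.2% | 57.9% | 19.0-23.3 |
| 200 | 0.25 | 94.8% | 81.6% | 77.6% | 13.2-17.2 |
| 200 | 0.35 | 99.9% | 98.4% | 97.3% | 1.6-2.6 |

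The loss therefore runs from about 2 to 23 points. A simulation (4,000 runs, Pearson test against logistic Wald test, r = 0.15-0.30) gave about 6 to 26.

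**4. Predictive performance.** Simulations used 134 development patients, a bounded 21-level pain score, 8 or 13 predictors and an assumed R² of 0.15 or 0.25. Each model predicted the same 15-point success out of sample. With ridge penalties on both models, the full-score fit was better in all eight settings: AUC higher by 0.008-0.019 and Brier score lower by 0.003-0.008.

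**The case against.** Several points on the other side are sound.

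- **Technique is left open.** Section 10.3 leaves the modelling technique to later decision and the algorithms to an SAP that is not shown, and a success label suits the stated purpose. Deriving the probability from a full-score model is not excluded. But the outcomes named in 10.3 and the event-based sizing in 4.4 are already fixed as binary.
- **Penalisation is allowed.** A reader might infer that the planned model would predict worse than quoting the overall success rate. An unpenalised logistic fit with 13 predictors can do so: at about 39% success and R² 0.15, its Brier score was 0.242 against 0.238 for no model. That is not the plan. Section 4.4 allows penalisation, and ridge on the cut outcome gave 0.231 and beat no model in all eight settings. Also, 13 predictors presuppose 67 events, while 134 × 0.39 is about 52. Penalisation narrows the gap but does not restore the discarded information.
- **Uncut pain is analysed.** A reader might infer that bone markers are never related to the full score. Section 4.4 does this in the exploratory secondary aim, with the same parameters. That analysis is not the prediction model and does not improve its predictions.
- **The 30-50% range is not specific to pain.** The 30% end may belong to the composite, so the 42% figure is conditional. The 36% floor is not affected by this.
- **A pain model cannot give radiographic or composite success.** This stands, and the point is limited to the clinical outcome.
- **The simulated data favour the linear model.** They were generated as linear and normal before the score was bounded, so the gains should be read as modest.

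**Conclusion.** The point holds as a cheap improvement to the substudy's primary aim. It does not make the planned model invalid. The firm part is the information loss: at least about 36%, and 36-42% if the pain label falls in the 30-50% range, assuming a roughly normal outcome and a weak marker.

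A reader might infer a fixed loss of power, for example 11 to 22 points. The Protocol does not support one: it states no marker effect, a range near that fits only mid-sized correlations of about 0.15-0.25, and significance of a single marker is not how section 10.3 chooses models. Over r = 0.10-0.35 the loss is about 2 to 23 points. The predictive gain is small but in one direction throughout, under assumed inputs. Missing two-year data are not replaced (section 8.5), so the numbers analysed are likely to fall below 200 and 134.

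**What to change.** **Section 10.3.** Fit the clinical model to the 24-month WOMAC pain score on its full scale, with baseline WOMAC pain as covariate. Use a linear model, or an ordinal one if ceiling effects are marked, penalised as section 4.4 already allows. From it, calculate each patient's probability of at least 15 points improvement. With a linear fit this is 1 − Φ[(baseline + 15 − predicted score) / residual SD]. Any stricter pain cut follows by replacing 15. Keep the 15-point label for reporting and for checking discrimination and calibration in the validation third.

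**Section 4.4.** For this model, count patients per predictor instead of events per predictor; 134 patients and 13 predictors give 134 / 13 = 10.3. Event counts remain relevant for the radiographic and composite models, which can stay as planned.

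**Cost.** Protocol and SAP wording only; no new patients, visits or measurements. The one downside is that the derived probability depends on the residual distribution. The calibration check would show a misfit, and an ordinal model avoids the normality assumption.
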